### 17.3.2. DAIDS TOXICITY GRADES

Quantitative laboratory parameters with available DAIDS toxicity grades will be categorized as follows where higher grades representing a more severe toxicity (refer to APPENDIX 4 for each parameter toxicity grade criteria):

- Grade 1 (i.e., mild);

Document: \[REDACTED]\net\enterprise\Apps\sasdata\SASB\SAS\Atea\_Pharmaceuticals\AT-527\{SZA63631\}\Biostatistics\Documentation\SAP\AT-03A-001\_V1.0\_COVID\_SAP\_PA7.doc  
Author: \[REDACTED] Version Number: V1.0

Template No.: CS\_TP\_BS016 Revision 6

Effective Date: 02Dec2019

Reference: CS\_WI\_BS005

Copyright © 2009, 2010, 2012, 2016, 2018

proprietary to [REDACTED] Holdings

or reproduction is strictly prohibited.

Copyright © 2009, 2010, 2012, 2016, 2018, 2019 [REDACTED] All rights reserved. The contents of this document are confidential and proprietary to [REDACTED] Holdings Inc. and its subsidiaries. Unauthorized use, disclosure or reproduction is strictly prohibited.

- Grade 2 (i.e., moderate);
- Grade 3 (i.e., severe)
- Grade 4 (i.e., potentially life-threatening)

Although not defined in the DAIDS toxicity grading system, version 2.1, non-missing laboratory parameter results not meeting any of the 4 grades defined in the DAIDS toxicity grading system will be categorized as having a Grade 0 (No Event) for the purpose of the shift from baseline summaries.

### 17.3.3. LABORATORY NORMAL RANGES

Quantitative laboratory parameters will be compared with the relevant laboratory normal ranges in SI units and categorized as:

- Low: Below the lower limit of the laboratory normal range.
- Normal: Within the laboratory normal range (upper and lower limit included).
- High: Above the upper limit of the laboratory normal range.

## 17.4. VITAL SIGNS

The following vital sign parameters will be collected for this study as per the schedule of events (refer to protocol, Section 6.3 and 6.7):

- Systolic blood pressure (SBP) (mmHg);
- Diastolic blood pressure (DBP) (mmHg);
- Pulse rate (beats per minute [bpm]);
- Oxygen saturation (%);
- Respiratory rate (breaths/min);
- Body temperature (° C);
- Weight (kg);

Document: \[REDACTED]\net\enterprise\Apps\sasdata\SASb\SAS\Atea\_Pharmaceuticals\AT-

527\5ZA63631\Biostatistics\Documentation\SAP\AT-03A-001\_V1.0\_COVID\_SAP\_PA7.doc

Author: \[REDACTED]

Version Number: V1.0

Version Date: 15Apr2021

Template No.: CS\_TP\_BS016 Revision 6

Reference: CS\_WI\_BS005

Effective Date: 02Dec2019

Copyright © 2009, 2010, 2012, 2016, 2018, 2019 \[REDACTED] All rights reserved. The contents of this document are confidential and proprietary to \[REDACTED] Holdings Inc. and its subsidiaries. Unauthorized use, disclosure or reproduction is strictly prohibited.

The following summaries will be provided by treatment group based on the SAF analysis set for each vital sign parameter:

- Observed and change from baseline by visit;
- Number and percentages of subjects with at least one markedly abnormal post-baseline observed value/change from baseline (refer to Section 17.4.1);
- Listing of subjects with at least one markedly abnormal observed value/change from baseline (refer to Section 17.4.1).

All vital sign data will be listed.

#### 17.4.1. VITAL SIGNS MARKEDLY ABNORMAL CRITERIA

Markedly abnormal vital sign observed values and/or change from baseline will be identified in accordance with the following predefined markedly abnormal criteria:

Variable	Unit	Low	High
SBP	mmHg	$\leq 90$ mmHg AND change from baseline $\leq -20$ mmHg	$\geq 180$ mmHg AND change from baseline $\geq 20$ mmHg
DBP	mmHg	$\leq 50$ mmHg AND change from baseline $\leq -15$ mmHg	$\geq 105$ mmHg AND change from baseline $\geq 15$ mmHg
Pulse rate	bpm	$\leq 50$ bpm AND change from baseline $\leq -15$ bpm	$\geq 120$ bpm AND change from baseline $\geq 15$ bpm
Oxygen saturation	%	$< 93$ %	Not applicable
Body temperature	°C	Not applicable	$\geq 38.3$ °C AND change from baseline $\geq 1.1$ °C
Weight	kg	Percent change from baseline $\leq -7.0$ %	Percent change from baseline $\geq 7.0$ %

Document: \\[REDACTED]\net\enterprise\Apps\sasdata\SASb\SAS\Atea\_Pharmaceuticals\AT-527\SAZ63631\Biostatistics\Documentation\SAPIAT-03A-001\_V1.0\_COVID\_SAP\_PA7.doc

Author: [REDACTED] Version Number: - V1.0  
Version Date: 15Apr2021

Template No.: CS\_TP\_BS016 Revision 6

Reference: CS\_WI\_BS005

Effective Date: 02Dec2019

Volume 59 Number 4 December 2004

Copyright © 2009, 2010, 2011

Copyright © 2005, 2010, 2012, 2010, 2010, 2013. All rights reserved. The contents of this document are confidential and proprietary to [REDACTED] Holdings Inc. and its subsidiaries. Unauthorized use, disclosure or reproduction is strictly prohibited.

## 17.5. ECG EVALUATIONS

The following electrocardiogram (ECG) parameters will be measured for this study as per the schedule of events (refer to protocol, Section 6.4):

- Heart rate (bpm);
- PR interval (msec);
- RR interval (msec);
- QRS interval (msec);
- QT interval (msec);
- QTc interval (msec);
- QTcF interval (msec);
- QTcB interval (msec);
- Overall ECG interpretation (Investigator's judgment):
  - Normal;
  - Abnormal, not clinically significant (NCS);
  - Abnormal, clinically significant (CS)

The following summaries will be provided by treatment group based on the SAF analysis set for each ECG parameter:

- Observed and change from baseline by visit (for quantitative parameters);
- Number and percentages of subjects with at least one markedly abnormal post-baseline observed value/change from baseline (for quantitative parameters; refer to [Section 17.5.2](#));
- Listing of subjects with at least one markedly abnormal observed value/change from baseline;

Document: \[REDACTED]\net\enterprise\Apps\sasdata\SASb\SAS\Atea\_Pharmaceuticals\AT-527\SAZ\A63631\Biostatistics\Documentation\SAP\AT-03A-001\_V1.0\_COVID\_SAP\_PA7.doc

Author: \[REDACTED] Version Number: V1.0  
Version Date: 15Apr2021

Template No.: CS\_TP\_BS016 Revision 6

Reference: CS\_WI\_BS005

Effective Date: 02Dec2019

Copyright © 2009, 2010, 2012, 2016, 2018, 2019 \[REDACTED] All rights reserved. The contents of this document are confidential and proprietary to \[REDACTED] Holdings Inc. and its subsidiaries. Unauthorized use, disclosure or reproduction is strictly prohibited.

COVID-19 Statistical Analysis Plan

ATEA Pharmaceuticals  
Protocol AT-03A-001  
Page 55 of 77

- Shift from baseline in overall ECG interpretation to the worst post-baseline assessment;
- Listing of subjects with at least one abnormal overall ECG interpretation, including the finding(s) for each subject

All ECG data will be listed.

### 17.5.1. ECG SPECIFIC DERIVATIONS

QTc Bazett's Correction (msec) will be computed as follows:

- $$QTcB \text{ (msec)} = \frac{QT \text{ (ms)}}{\sqrt{RR \text{ (ms)}}/1000}$$

### 17.5.2. ECG MARKEDLY ABNORMAL CRITERIA

Markedly abnormal quantitative ECG parameters will be identified in accordance with the following predefined markedly abnormal criteria:

- Observed values for QTc, QTcF, and QTcB intervals will be classified as:
  - > 450 msec;
  - > 480 msec;
  - > 500 msec
- Change from baseline for QTc, QTcF, and QTcB intervals will be classified as:
  - >30 msec increase from baseline
  - >60 msec increase from baseline

It is to be noted that the previous categories are not mutually exclusive, but cumulative. For example, if a subject worst post-baseline QTc post-baseline observed value is 490 mmHg, then this subject will be reported once under QTc > 450 msec and once under QTc > 480 msec.

Document: \[REDACTED]\net\enterprise\Apps\sasdata\SASb\SAS\Atea\_Pharmaceuticals\AT-527\SAZ63631\Biostatistics\Documentation\SAP\AT-03A-001\_V1.0\_COVID\_SAP\_PA7.doc

Author: \[REDACTED] Version Number: V1.0  
Version Date: 15Apr2021

Template No.: CS\_TP\_BS016 Revision 6

Reference: CS\_WI\_BS005

Effective Date: 02Dec2019

Copyright © 2009, 2010, 2012, 2016, 2018, 2019 \[REDACTED] All rights reserved. The contents of this document are confidential and proprietary to \[REDACTED] Holdings Inc. and its subsidiaries. Unauthorized use, disclosure or reproduction is strictly prohibited.

## 17.6. PHYSICAL EXAMINATION

### 17.6.1. GENERAL PHYSICAL EXAMINATION

Physical examinations will be conducted as per the schedule of events (refer to protocol Section 6.2).

The following summaries will be provided by treatment group based on the SAF analysis set for physical examination data:

- Incidence of abnormalities at screening and each post-screening visit

All physical examination data will be listed.

### 17.6.2. CHEST IMAGING

Chest imaging will be performed as per the schedule of events (refer to protocol Section 6.8).

Number and percentage of subjects with normal, abnormal NCS, and abnormal CS chest imaging result, as per the Investigator's judgment, will be provided by treatment group and visit based on the SAF analysis set.

All chest imaging data, including findings, will be listed.

## 18. DATA NOT SUMMARIZED OR PRESENTED

Data that will not be summarized or listed are:

- Comments

These data will not be summarized or listed but will be available in the Study Data Tabulation Model (SDTM) and/or Analysis Dataset Modelling (ADaM) datasets.

Document: \\[REDACTED]\net\enterprise\Apps\sasdata\SASb\SAS\Atea\_Pharmaceuticals\AT-527\SAZ\A63631\Biostatistics\Documentation\SAP\AT-03A-001\_V1.0\_COVID\_SAP\_PA7.doc  
Author: [REDACTED] Version Number: V1.0  
Template No.: CS\_TP\_BS016 Revision 6 Version Date: 15Apr2021  
Effective Date: 02Dec2019 Reference: CS\_WI\_BS005

Copyright © 2009, 2010, 2012, 2016, 2018, 2019 [REDACTED] All rights reserved. The contents of this document are confidential and proprietary to [REDACTED] Holdings Inc. and its subsidiaries. Unauthorized use, disclosure or reproduction is strictly prohibited.

## COVID-19 Statistical Analysis Plan

ATEA Pharmaceuticals  
Protocol AT-03A-001  
Page 58 of 77

## APPENDIX 1. PARTIAL DATE CONVENTIONS

## ALGORITHM FOR TREATMENT EMERGENCE OF ADVERSE EVENTS

START DATE	END DATE	ACTION
Known	Known/Partial/ Missing	If (AE start date/time < study drug start date/time), then not TEAE;  If study drug start date/time $\leq$ AE start date/time $\leq$ 28 days after last drug date, then TEAE.
Partial, but known components show that AE started before study drug start date	Known/Partial/ Missing	Not TEAE.
Partial, but known components show that AE started on or after date of first dose of study drug and AE start date $\leq$ 28 days after last drug date	Known/Partial/ Missing	Assume TEAE.
Missing	Known	If (AE end date/time < study drug start date/time) , then not TEAE;  Otherwise, TEAE.
	Partial	If known components of AE end date/time show that AE stopped before study drug start date/time), then not TEAE;  Otherwise, TEAE.
	Missing	Assume TEAE.

Document: \\[REDACTED]\net\enterprise\Apps\sasdata\SASb\SAS\Atea\_Pharmaceuticals\AT-527\SAZ63631\Biostatistics\Documentation\SAPIAT-03A-001\_V1.0\_COVID\_SAP\_PA7.doc

Author: [REDACTED] Version Number: V1.0  
Version Date: 15Apr2021

Template No.: CS\_TP\_BS016 Revision 6

Reference: CS\_WI\_BS005

Effective Date: 02Dec2019

Version Date: 15Apr2021

Copyright © 2009, 2010, 2012, 2016, 2018

Reference: CS\_WI\_BS005

Copyright © 2009, 2010, 2011  
Proprietary to [REDACTED] Holdings

Copyright © 2005, 2010, 2012, 2010, 2018, 2019 [REDACTED] All rights reserved. The contents of this document are confidential and proprietary to [REDACTED] Holdings Inc. and its subsidiaries. Unauthorized use, disclosure or reproduction is strictly prohibited.

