The start date of an SAE reported on the Serious Adverse Event form must be the same as the start date of the corresponding AE documented on the eCRF. If a change in severity is noted for the existing AE, it must be recorded. If a worsened AE meets the criteria for an SAE, the start date of the SAE must be the same as the start date of the worsened AE.

All SAEs that have not resolved by the end of the study, or that have not resolved upon discontinuation of the subject’s participation in the study, must be followed until any of the following occurs:

- the event resolves;
- the event stabilizes;
- the event returns to baseline, if a baseline value is available;
- the event can be attributed to agents other than the study drugs or to factors unrelated to study conduct;
- it becomes unlikely that any additional information can be obtained (subject or health care practitioner refusal to provide additional information, lost to follow-up after demonstration of due diligence with follow-up efforts).

Any SAE reports will be reported by the investigators (or designee) to their local IRB/IEC in accordance with local reporting requirements and reporting timelines.

Similarly, the Sponsor (or designee) will determine whether an SAE must be reported in an expedited manner to regulatory authorities, in accordance with regulatory requirements. If so, the Sponsor (or designee) will report the event to the regulatory authorities in accord with applicable reporting timelines.

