8.4. Safety and PK Analyses

Safety Analyses

Assessing safety and tolerability of AT-527 at the selected dose will be an important objective of the study.

Protocol Number: AT-03A-001

Proportions of subjects experiencing SAEs, AEs, AEs resulting in treatment discontinuation and graded laboratory abnormalities will be summarized. Treatment-emergent AEs and laboratory abnormalities, defined as post-Baseline new AEs or worsened AEs, or new or worsening laboratory parameters, beginning with or after the first dose of study drug, will be included in the safety analyses. These safety-related observations will be summarized by treatment group, primarily using descriptive statistics, with use of time-to-event sub-analyses when appropriate for comparative time-related analyses of any specific clinically severe findings (e.g. death, SAEs, grade 3-4 AEs, or clinically significant grade 3-4 laboratory abnormalities).

Laboratory, ECG and vital sign data will also be summarized with descriptive statistics.

Descriptive statistics will also be used to summarize demographic variables. Other data to be summarized will include medical history, physical examination findings and concomitant medications.

PK Analyses

Plasma concentrations of study drug and metabolites in sparse samples will be listed with time data and summarized using descriptive statistics, as applicable.

Additional details regarding safety and PK analyses will be provided in the SAP.

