### 6.2. BASELINE

Unless otherwise specified, baseline is defined as the last non-missing measurement taken prior to the first dose of study drug (including unscheduled assessments). In the case where the last non-missing measurement and the date and time of the first dose of study drug coincide, that measurement will be considered pre-baseline. In cases where the time is missing, and the last non-missing measurement and the date of the first dose of study drug coincide, that measurement will be considered pre-baseline.

Adverse event (AE) start date and time is to be collected. Any adverse event with start date and time prior to the date and time of first study drug administration will be considered as a baseline sign/symptom. An adverse event starting on the date of first dose of study drug with missing start time or with start time the same as or after the start time of the first study drug administration will be considered treatment-emergent, i.e. post-baseline.

Document:	\[REDACTED]\net\enterprise\Apps\sasdata\SASb\SAS\Atea_Pharmaceuticals\AT-527\ISZA63631\Biostatistics\Documentation\SAP\AT-03A-001_V1.0_COVID_SAP_PA7.doc		
Author:	\[REDACTED]	Version Number:	V1.0
		Version Date:	15Apr2021
Template No.:	CS_TP_BS016 Revision 6	Reference:	CS_WI_BS005

Effective Date: 02Dec2019

Copyright © 2009, 2010, 2012, 2016, 2018, 2019 \[REDACTED] All rights reserved. The contents of this document are confidential and proprietary to \[REDACTED] Holdings Inc. and its subsidiaries. Unauthorized use, disclosure or reproduction is strictly prohibited.

Medications starting on the date of first dose of study drug will be considered post-baseline.

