#### 17.1. ADVERSE EVENTS

- Prior AEs are defined as any AE that started or worsened in severity on or after the date of signed informed consent but before the first dose of study drug.

Document: \[REDACTED]\net\enterprise\Apps\sasdata\SASb\SAS\Atea\_Pharmaceuticals\AT-527\SAZ\A63631\Biostatistics\Documentation\SAP\AT-03A-001\_V1.0\_COVID\_SAP\_PA7.doc  
Author: \[REDACTED]

Version Number: V1.0  
Version Date: 15Apr2021

Template No.: CS\_TP\_BS016 Revision 6

Reference: CS\_WI\_BS005

Effective Date: 02Dec2019

Copyright © 2009, 2010, 2012, 2016, 2018, 2019 \[REDACTED] All rights reserved. The contents of this document are confidential and proprietary to \[REDACTED] Holdings Inc. and its subsidiaries. Unauthorized use, disclosure or reproduction is strictly prohibited.

- Treatment emergent AEs (TEAEs) are defined as any AE that started or worsened in severity on or after the first dose of study drug but no later than 28 days after the last dose of study drug. Events considered as possibly related to study drug that occur in follow-up more than 28 days after last study drug will also be considered TEAE.

See APPENDIX 1 for handling of partial dates for AEs. In the case where it is not possible to define an AE as treatment emergent or not, the AE will be classified by the worst case; i.e. treatment emergent.

AEs will be coded using the MedDRA dictionary, version 23.0.

An overall summary of number and percentage of subjects within each of the categories described in the sub-sections below will be provided by treatment group based on the SAF analysis set. Should a subject experience multiple event within a category, the subject will be counted only once for that category.

All AEs (prior and TEAE) will be listed.

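### SAP Appendix 1 and SAP 6.2 decide treatment emergence by AE start date alone, contradicting SAP 17.1 and Protocol 8.4, which also count AEs that worsen after the first dose

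*SAP*

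**What the plan says.** **Definition.** SAP 17.1 defines a TEAE as "any AE that started or worsened in severity on or after the first dose of study drug". It sets a cut-off of 28 days from the final dose, and also admits later events judged possibly related to study drug. Protocol 8.4 agrees that worsening counts: its treatment-emergent events are "defined as post-Baseline new AEs or worsened AEs" from the first dose on.

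**Algorithm.** SAP Appendix 1 turns this into rows by type of start date. For a fully known start it says "If (AE start date/time < study drug start date/time), then not TEAE". A second row, "Partial, but known components show that AE started before study drug start date", also gives not TEAE. Neither row asks whether severity later increased.

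**Baseline rule.** SAP 6.2, in the main text, says that an AE starting "prior to the date and time of first study drug administration will be considered as a baseline sign/symptom". It too is silent on later worsening.

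**Recording.** AEs are collected from informed consent (Protocol 7.2). Protocol 7.3 says: "If a change in severity is noted for the existing AE, it must be recorded". It does not say whether the change gets its own record or its own date.

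**Later changes.** The Changes to Planned Statistical Analyses Form of 16 March 2022 does not touch the algorithm, and it states that the SAP will not be revised.

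**The concern.** The definition has two limbs, onset and worsening, and the algorithm implements only the first. An AE that starts after consent but before dosing and becomes more severe on study drug is a TEAE under SAP 17.1 and Protocol 8.4, but not under Appendix 1. A programmer who codes the appendix and one who codes the definition would produce different tables from the same data.

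What is at stake is the by-arm AE counts. The changes form drops the TEAE summaries by relationship to study and non-study treatment, the summary of TEAEs leading to study discontinuation, and the death summary. It does not drop the all-TEAE summary, maximum severity, serious TEAEs, TEAEs with a fatal outcome, or TEAEs leading to drug withdrawal. All of these rest on the TEAE flag. An omitted worsening could fall in either arm, so the effect has no fixed direction.

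**Working it through.** The plan gives no figure to reproduce for this point. The check is to run each type of event through both rules.

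| Case | SAP 17.1 / Protocol 8.4 | Appendix 1 |
|---|---|---|
| (a) Onset between consent and first dose; worsens after dosing but stays non-serious; same record kept | TEAE, through the worsening limb | Not TEAE |
| (b) As (a), but worsens to serious | TEAE | Depends on the start date assigned (see below) |
| (c) Earlier chronic or concomitant illness that worsens after dosing | TEAE | TEAE if dated from the worsening, because Protocol 7.1 makes such worsening an AE in its own right |
| (d) AE start date missing | Worst-case rule if status cannot be determined | TEAE unless the end date is shown to precede dosing |
| (e) Starts on the first-dose date with no time recorded | TEAE under SAP 6.2 | No separate row for a missing time |

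**Case (a)** is a direct contradiction. The worst-case clause in SAP 17.1 does not remove it, because that clause applies only when status cannot be determined. A known pre-dose start gives a definite answer under Appendix 1.

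**Case (b)** is unresolved. Protocol 7.3 has a non-serious AE that worsens to serious reported as a new SAE, and ties the SAE start date to the start date of the worsened AE. If that means the date of worsening, Appendix 1 also returns TEAE. If it means the onset date on the existing AE record, the serious worsening is lost too. The text allows both readings.

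**Cases (c) to (e)** show no loss provided that, in (c), the AE is dated from the worsening. They limit the problem to AEs that began after consent and before dosing.

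**Size of one event, Part A.**
- 81 subjects were randomised 1:1 (Protocol 3.1 and 3.2), so 81 / 2 = 40.5 per arm. This assumes an even split with all subjects treated.
- One subject moved in or out of a TEAE category changes that arm's rate by 1 / 40.5 = 0.0247, about 2.5 percentage points.

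This is the weight of one subject. It does not estimate how many are affected. The documents give no AE counts by onset and worsening, so that number cannot be computed.

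**The case against.** **Precedence.** The strongest reply is that SAP 17.1 holds the definition and sends the reader to the appendix only for incomplete dates: "See APPENDIX 1 for handling of partial dates for AEs". SAP 7.2 does the same, and the appendix is titled as partial-date conventions. Nothing says that it overrides 17.1, so the loss arises only if a programmer follows the algorithm over the definition. That condition stands, and the conclusion is worded accordingly. It does not settle the matter. The algorithm's first row governs fully known start dates, and SAP 6.2 puts the same start-only rule in the main text. Two places in the SAP point one way and one points the other.

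**Few events.** Dosing should follow confirmed eligibility within 24 hours, and Screening and Day 1 may fall on the same day (Protocol 6). This largely stands, although that clock runs from eligibility and AE collection runs from consent. Laboratory changes without clinical significance are not recorded as AEs at all (Protocol 7.1).

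**Still listed.** SAP 17.1 lists prior AEs as well as TEAEs, so no event disappears from the report. That stands, but a listing does not correct a by-arm count.

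**Stronger readings that the documents do not support.**
- A reader might infer that every pre-dose AE is excluded, or that worsened events vanish from all TEAE tables. Cases (b) to (d) rule that out: missing starts mostly default to TEAE, and worsening to serious generates a new SAE report whose dating is ambiguous.
- A reader might infer that worsening of the acute COVID-19 illness is removed from the safety counts. Protocol 7.1 makes worsening of a concomitant illness its own AE, and SAP Sections 11 and 12 place conditions and symptoms present at entry under medical and disease history. Their worsening can therefore enter as a new post-dose AE.
- A reader might extend the arithmetic to Part B, with up to 110 subjects, 55 per arm and 1/55 = 1.8 points. The changes form says that Part B patients are only listed, so there is no Part B rate to change, and 110 is a planned maximum.

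**Conclusion.** The contradiction is in current text, and neither the worst-case clause nor the March 2022 form resolves it. Followed as written, Appendix 1 leaves out of the by-arm TEAE summaries an AE with onset between consent and first dose whose severity increases after dosing and which stays on its existing record. This is certain when the worsening remains non-serious. When it becomes serious, the result depends on how Protocol 7.3 is read.

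The practical effect is probably small: few events, in an unknown number, all still listed, each weighing about 2.5 percentage points of a Part A arm on an even split of 81. The documents do not show that any event was in fact lost or that either arm was favoured. The point is still worth correcting, because a stated rule misclassifies events under the plan's own safety definition and the wording change is short.

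**What to change.** 1. In both Appendix 1 rows (known start before first dose, and partial start known to precede it) add a branch. If severity increases on or after the first dose and within the SAP 17.1 window, the AE is a TEAE with the date of the increase as its onset. Otherwise it is not a TEAE.
2. Add the same exception to the AE sentence in SAP 6.2.
3. State that a post-dose increase in severity is captured as a dated record. Protocol 7.3 asks for the change to be recorded but does not clearly ask for its date, and the new branch needs one. Where the date is missing, apply the SAP 17.1 worst-case rule and count the AE as a TEAE.
4. Because the changes form says that the SAP will not be revised, carry this wording in that form or an addition to it.

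**Cost.** Two table rows, one sentence in SAP 6.2 and one data-capture instruction. The downside is a few more TEAEs in the summaries and a little more programming or data-capture work, mainly to obtain dates for severity increases that were recorded without one.
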